### **2.7.3.1 Summary of absolute values**

For all continuous laboratory parameters, the absolute on-treatment laboratory values, including the worst case post-baseline values (including values from post-baseline unscheduled and premature discontinuation visits), will be summarized with standard descriptive statistics by parameter, scheduled visit and time-point, and treatment group.

The direction of interest for worst case post-baseline for selected hematology and biochemistry parameters is tabulated in [Table 6-4-1](#). For continuous urinalysis parameters, the direction of interest is always High.

A frequency table of results for categorical on-treatment laboratory parameters will be produced. For categorical urinalysis laboratory parameters, a frequency table of results will be produced by laboratory parameter, scheduled visit and time-point, and treatment. Worst-case on-treatment post-baseline values (including values from post-baseline unscheduled and premature discontinuation visits) will also be included.

For summary tables and figures on laboratory parameters considering values, which are lower or greater than the limit of quantification, the following approach will be taken. For values which are flagged as lower than the lower limit of quantification, the values presented in summary tables should be multiplied by 0.5 and for values that are flagged as greater than upper limit of quantification as 1.5, the values presented in summary tables should be multiplied by 1.5.

### **2.7.3.2 Summary of change from baseline**

For continuous laboratory parameters, the on-treatment change from baseline at each scheduled visit and time-point, and the on-treatment change from baseline to the worst case post-baseline values (including values from post-baseline unscheduled and premature discontinuation visits) will be summarized by laboratory parameter, scheduled visit and time-point, and treatment group with standard descriptive statistics.

In order to observe the tendency of treatment effect on mean values, box plots by treatment arm for post-baseline values and worst case post-baseline will be presented on the change from baseline for all laboratory parameters. Albumin: Creatinine ratio (ACR) value will be considered missing if either the albumin or the creatinine values are missing. Similarly, Protein: Creatinine ratio (PCR) will be considered missing if either the protein or the creatinine values are missing.

#### Liver function tests

To evaluate potential drug-induced liver injury, newly occurring or worsening abnormalities in liver function tests will be evaluated (see [Table 6-4-3](#) for a summary of the notable values).

When a criterion contains multiple laboratory parameters, the criterion will only be considered to be met when all conditions occur at the same time (i.e., in the same sample). A case where all criteria are met at a post-baseline time point but not met at baseline will be considered as newly occurring. A case will be considered as worsening if all the criteria are met at baseline and at least one component is worsening from baseline, irrespective of whether the other(s) are better.

The number and percentage of patients with newly occurring liver enzyme abnormalities any time post-baseline will be summarized. Listings of patients with notable liver function test lab values and liver events will be provided.

To evaluate drug induced serious hepatotoxicity eDish plots will be presented. The eDish plot will reflect the worst value of each of the parameters; they do not need to occur at the same visit.

## 2.7.4 Other safety data

### 2.7.4.1 ECG data

ECG measurements include heart rate, QT interval, RR interval, PR interval, QRS duration, and Fridericia's QTc (calculated as  $QTcF = QT / \sqrt[3]{RR}$  (in seconds), where  $\sqrt[3]{}$  denotes the cube root). Furthermore, an overall interpretation of the central cardiologist will be provided as well as a specification of abnormal findings.

ECG data measured more than 7 days after last intake of study drug are regarded as post treatment data and will not be summarized. All data will be included in the analyses regardless of rescue medication use.

### Summary of absolute values and change from baseline

Absolute values and change from baseline summarized by parameter, and visit.

#### Clinically notable values

- The number and percentage of patients with newly occurring or worsening clinical notable QTcF values (see Table 2-3) summarized by scheduled post-baseline visit and additionally at any time on treatment considering all post-baseline data from scheduled, unscheduled and premature discontinuation visits.

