Data of the vital signs (systolic blood pressure, diastolic blood pressure, and pulse rate) will be summarized by treatment and scheduled visit. The maximum and minimum systolic blood pressure, diastolic blood pressure, and pulse rate post-baseline (including values from post-baseline unscheduled and premature discontinuation visits) can also be summarized by treatment. Absolute body weight will be summarized by scheduled visit. The change from baseline to each scheduled post-baseline visit will be summarized by vital sign parameter, scheduled visit and treatment with standard descriptive statistics.

Notable values and notable changes from baseline in vital signs will be summarized.

9.5.2.3 **Electrocardiogram (ECG)**

The changes from baseline will be summarized by ECG parameter, schedule visit where baseline and post baseline values are both available.

The following quantitative variables will be summarized by treatment at each scheduled post-baseline visit: ventricular rate, QT interval, RR interval, PR interval, QRS duration, heart rate, and Fridericia's QTc. The maximum QTc (including values from post-baseline unscheduled and premature discontinuation visits) will also be summarized.

Notable values and notable changes from baseline in quantitative ECG variables will be summarized.

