

13 Appendix 1: Clinically notable laboratory values and vital signs

The central laboratory will flag laboratory values falling outside of the normal ranges on the central laboratory reports. Investigators are responsible for reviewing these abnormal values for clinical significance, signing the laboratory reports to indicate their review, and reporting values considered clinically significant in the appropriate electronic case report form (eCRF).

Any clinically significant abnormal laboratory value should be evaluated and followed-up by the investigator until normal or a cause for the abnormality is determined.

See [Appendix 2](#) for specific liver event and laboratory test trigger definitions and follow-up requirements. See [Appendix 3](#) for specific renal alert criteria and actions.

For electrocardiograms (ECGs), a notable QTc value is defined as a QTcF (Fridericia) interval of ≥ 450 msec for males or ≥ 460 msec for females – all such ECGs will be flagged by the Central contract research organization (CRO) and require assessment for clinical relevance and continuance of the patient by the Investigator.

14 Appendix 2: Liver event and laboratory trigger definitions and follow-up requirements

Table 14-1 Liver Event and Laboratory Trigger Definitions

	Definition/ threshold
LIVER LABORATORY TRIGGERS	3 x ULN < ALT / AST ≤ 5 x ULN 1.5 x ULN < TBL ≤ 2 x ULN
LIVER EVENTS	ALT or AST > 5 x ULN ALP > 2 x ULN (in the absence of known bone pathology) TBL > 2 x ULN (in the absence of known Gilbert syndrome) ALT or AST > 3 x ULN and INR > 1.5 Potential Hy's Law cases (defined as ALT or AST > 3 x ULN and TBL > 2 x ULN [mainly conjugated fraction] without notable increase in ALP to > 2 x ULN) Any clinical event of jaundice (or equivalent term) ALT or AST > 3 x ULN accompanied by (general) malaise, fatigue, abdominal pain, nausea, or vomiting, or rash with eosinophilia Any adverse event potentially indicative of a liver toxicity*

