**Table 2-3 Clinically notable criteria for QTcF (Fridericia's formula)**

ECG parameter (unit)	Clinically notable range
Value considering newly occurring or worsening cases	
QTc (msec)	≥ 450 (male)
QTc (msec)	≥ 460 (female)
QTc (msec)	> 500 (both)
Change from baseline	
QTc	1 - < 30
QTc	30 – 60
QTc	> 60

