#### Clinically relevant values

- A summary table will also be produced for number and percentage of subjects with clinically relevant QT and QTcF intervals (irrespective of the time point) using the following categories:
  - any treatment emergent (new) QTcF ≥ 450 ms – 480 ms, > 480 ms – 500 ms or > 500 ms
  - QTcF increase from baseline of 30 ms – 60 ms, > 60 ms
  - QTcF increase from baseline of ≥ 30 ms plus QTcF interval ≥ 450 ms, > 480 ms or > 500 ms

- d. QTcF increase from baseline of  $\geq 60$  ms plus QTcF interval  $\geq 450$  ms,  $> 480$  ms or  $> 500$  ms
- The number and percentage of subjects with noteworthy PR, QRS and HR interval changes will be reported using the below categories:
  - a. New PR  $> 200$  ms to  $\leq 220$  ms; and  $> 220$  ms
  - b. New QRS  $> 110$  ms to  $\leq 120$  ms; and  $> 120$  ms
  - c. PR increase  $> 25\%$  to a value  $> 200$  ms
  - d. QRS increase  $> 25\%$  to a value  $> 120$  ms
  - e. HR decrease  $> 25\%$  to a HR  $< 50$  bpm
  - f. HR increase  $> 25\%$  to a HR  $> 100$  bpm

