### Overall ECG interpretation

- Summary of ECG abnormalities will be produced on following variables: The number and percentage of subjects with newly occurring or persistent/recurrent on-treatment ECG abnormalities in overall ECG interpretation at any time point
    - The number and percentage of subjects with newly occurring or persistent/recurrent on-treatment ECG abnormalities by evaluation type and abnormality finding at any time point.
- If patients had at least once ECG abnormality at baseline, the baseline flag will be abnormal. Similarly, for post baseline visits, if patients had at least once ECG abnormality at a visit, then ECG is abnormal at that visit else normal.
- Patients with notable post-baseline ECG values will be listed. Box plots of ECG by scheduled visit and treatment for the parameters: QTcF and summary (mean) heart rate will be presented.

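### The SAP drops, without declaring it, the protocol's summary of maximum post-baseline QTc, and its Table 2-3 labels a QTcF rise of 1 to <30 ms clinically notable

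*SAP*

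**What the plan says.** **Continuous QTc.** Protocol Section 9.5.2.3 asks for ECG variables by scheduled visit and then adds: "The maximum QTc (including values from post-baseline unscheduled and premature discontinuation visits) will also be summarized". For continuous ECG data, SAP Section 2.7.4.1 has: "Absolute values and change from baseline summarized by parameter, and visit". It also plans box plots of QTcF by scheduled visit, and it does not summarize ECGs taken more than 7 days after the last dose. It contains no maximum. The visible text of SAP Section 4 (changes to the protocol analyses) drops ECG shift tables but does not mention the maximum QTc.

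**ECG timing.** Protocol Table 6-1 schedules ECGs at Visit 1, Visit 201, the treatment discontinuation (TD) visit and Visit 299. Only the last two are post-baseline. Under SAP Section 6.3, a TD visit can stand in for a missed scheduled visit if that visit's planned day is the nearest one. Otherwise it is left out of by-visit summaries.

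**Categorical QTc.** The SAP counts "The number and percentage of patients with newly occurring or worsening clinical notable QTcF values (see Table 2-3) summarized by scheduled post-baseline visit". The same sentence goes on to a second count over the whole on-treatment period, which also draws on unscheduled ECGs and on those taken at early discontinuation. The table it cites is titled "Clinically notable criteria for QTcF (Fridericia's formula". That table has a block of absolute values (450 ms male, 460 ms female, 500 ms both) and a block of changes from baseline with three rows: 1 to <30, 30 to 60 and >60 ms. The next list, of clinically relevant values at any time point, has "QTcF increase from baseline of 30 ms – 60 ms, > 60 ms" and no lower category.

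**Listing and definition.** The SAP states: "Patients with notable post-baseline ECG values will be listed". Protocol Appendix 1 says: "a notable QTc value is defined as a QTcF (Fridericia) interval of ≥ 450 msec for males or ≥ 460 msec for females". The protocol also asks for notable changes to be summarized but gives no ms limit for a change.

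**The concern.** Fridericia's QTc is a named secondary safety endpoint, and the protocol relies on ECGs to monitor cardiovascular risk. The maximum is the one continuous QTc statistic in the protocol that brings in patients who stop early. Without it, the continuous comparison rests mainly on patients still on drug at Week 12. An analysis that the protocol says will be done should also not disappear without an entry in the SAP's list of changes. The SAP keeps worst-case post-baseline summaries, including discontinuation visits, for laboratory data (Sections 2.7.3.1 and 2.7.3.2), and minimum and maximum post-baseline categories for vital signs (Section 2.7.4.2). The gap for ECG therefore looks like an oversight.

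The label in Table 2-3 is a smaller matter. A 1 ms rise is called notable there and is below the lowest category in the list that follows. If the listing is built from that table, it would run to a large share of the trial and lose its use as a screening tool.

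**Working it through.** **A. Which early stoppers reach the Week 12 continuous summary?**

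Inputs: planned visits on Days 14, 28, 56 and 84 (Protocol Table 6-1); the nearest-day rule (SAP Section 6.3); the 7-day limit (SAP Section 2.7.4.1); 15% discontinuation and 650 patients (SAP Section 3).

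1. The midpoint between the last two planned visits is (56 + 84)/2 = Day 70. A TD visit before about Day 70 is nearer to an earlier visit and cannot become the Week 12 record. Those earlier visits have no scheduled ECG, so the TD value either appears at a visit where completers have no scheduled ECG or is treated as unscheduled and left out.
2. A patient who stops and still attends Visit 299 has an ECG on Day 84. If the last dose was before Day 84 − 7 = Day 77, that ECG is outside the window and is not summarized.
3. A patient who stops later can enter the Week 12 summary in two ways: Visit 299 is missed and the TD visit is re-mapped, or the last dose was on Day 77 or later and Visit 299 is attended.
4. Expected early stoppers: 0.15 × 650 = 97.5, about 98 (49 per arm). The documents do not give the timing of stopping. If it is even over 84 days, the share before Day 70 is 70/84 = 83%, and 0.83 × 97.5 is about 81 patients. If the share before Day 70 is anywhere from 50% to 95%, the number is 49 to 93.

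Their TD ECGs do count in the any-time tables when taken within 7 days of the last dose.

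**B. How many patients fall in the 1 to <30 ms row by chance?**

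The documents give no expected share and no SD of QTcF change, so there is no plan figure to reproduce. Assume no drug effect, one post-baseline ECG per patient (the schedule provides one on-treatment ECG, at Visit 299 or TD) and change ~ Normal(0, SD).

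Share in the row = Φ(30/SD) − Φ(1/SD). With whole-ms readings it is Φ(29.5/SD) − Φ(0.5/SD). Share at 30 ms or more = 1 − Φ(30/SD).

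| Assumed SD (ms) | 1 to <30 | Of 650 | 1 to <30, whole ms | ≥30, of 650 |
|---|---|---|---|---|
| 8 | 45.0% | 293 | 47.5% | 0.1 |
| 10 | 45.9% | 298 | 47.8% | 0.9 |
| 12 | 46.1% | 299 | 47.6% | 4.0 |
| 15 | 45.1% | 293 | 46.2% | 14.8 |
| 20 | 41.3% | 269 | 42.0% | 43.4 |

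Example, SD 10: Φ(3) − Φ(0.1) = 0.9987 − 0.5398 = 0.459, and 0.459 × 650 = 298.

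The range is 41–46% on the continuous scale and 42–48% in whole ms. At SD 25 the share is 36.9%. If patients had two post-baseline ECGs (assumed correlation 0.5), the any-time share would be 61–63% for SD 10 to 20.

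**The case against.** The strongest reply is that nothing important is lost. The sentence that defines the notable-value count goes on to include unscheduled and discontinuation visits, and the next list applies at any time point. A count above a threshold at any time is in effect a categorical summary of each patient's maximum. This stands. A reader might infer that the SAP loses early stoppers' QTcF altogether, and the documents do not support that. What is missing is the continuous statistic. Threshold counts do not fully replace it, because a modest average shift moves few patients across a limit. With an assumed SD of 15 ms, a 5 ms mean shift raises the share at 30 ms or more from 2.3% to 4.8%. Among about 49 stoppers per arm that is 49 × 0.023 = 1.1 against 49 × 0.048 = 2.4 patients.

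A reader might also infer that the 1 to <30 ms row hides real prolongations. It does not. The three change rows are reported separately, nothing in the SAP pools them, and the next list reports the larger changes again.

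Nor does the row contradict Protocol Appendix 1. The appendix defines a notable value, Table 2-3 repeats its 450 and 460 ms limits, and the protocol sets no limit for a change. The inconsistency is within the SAP.

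The listing sentence does not cite Table 2-3 and speaks of values, so it can fairly be read as using the absolute-value block only. It is ambiguous, and it cannot be said that half the patients will be listed.

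Finally, some lines in SAP Section 4 are blacked out, so only its visible text can be checked.

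**Conclusion.** Two minor defects hold.

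1. The protocol's maximum-QTc summary is absent from SAP Section 2.7.4.1, and its removal is not declared in the visible text of Section 4. As a result, most early stoppers' on-treatment QTcF stays out of the Week 12 continuous summary: about 81 of 98 if stopping is even over time, 49 to 93 if the share before Day 70 is 50–95%. These numbers rest on the planned 15% discontinuation and on assumed timing. The same patients remain in the any-time categorical tables, so this is a gap in one continuous comparison. The documents also give no support for a claim that a cardiac signal is most likely in these patients.

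2. Table 2-3 gives the label clinically notable to a change category that would hold about 41–48% of patients with no drug effect, assuming one post-baseline ECG and an SD of 8 to 20 ms. This is a labelling inconsistency with the SAP's own next list, plus an ambiguity in the listing. The counts at 30 to 60 and >60 ms are unaffected.

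The first is worth a specific change. The second is editorial.

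**What to change.** - In SAP Section 2.7.4.1, reinstate a summary by treatment of the maximum post-baseline on-treatment QTcF and its change from baseline, including unscheduled and TD visits. If the sponsor prefers not to do this, declare and justify the removal in SAP Section 4.
- In Table 2-3, show the 1 to <30 ms row as a change category that is not labelled notable, for example under a separate sub-heading.
- State that this row does not trigger the listing of patients with notable ECG values, and name the criteria that do.

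The cost is one extra table and two lines of SAP text. No new data are needed, and the change can be made before unblinding.

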**Table 2-3 Clinically notable criteria for QTcF (Fridericia's formula)**

ECG parameter (unit)	Clinically notable range
Value considering newly occurring or worsening cases	
QTc (msec)	≥ 450 (male)
QTc (msec)	≥ 460 (female)
QTc (msec)	> 500 (both)
Change from baseline	
QTc	1 - < 30
QTc	30 – 60
QTc	> 60

#### Clinically relevant values

- A summary table will also be produced for number and percentage of subjects with clinically relevant QT and QTcF intervals (irrespective of the time point) using the following categories:
  - any treatment emergent (new) QTcF ≥ 450 ms – 480 ms, > 480 ms – 500 ms or > 500 ms
  - QTcF increase from baseline of 30 ms – 60 ms, > 60 ms
  - QTcF increase from baseline of ≥ 30 ms plus QTcF interval ≥ 450 ms, > 480 ms or > 500 ms

- d. QTcF increase from baseline of  $\geq 60$  ms plus QTcF interval  $\geq 450$  ms,  $> 480$  ms or  $> 500$  ms
- The number and percentage of subjects with noteworthy PR, QRS and HR interval changes will be reported using the below categories:
  - a. New PR  $> 200$  ms to  $\leq 220$  ms; and  $> 220$  ms
  - b. New QRS  $> 110$  ms to  $\leq 120$  ms; and  $> 120$  ms
  - c. PR increase  $> 25\%$  to a value  $> 200$  ms
  - d. QRS increase  $> 25\%$  to a value  $> 120$  ms
  - e. HR decrease  $> 25\%$  to a HR  $< 50$  bpm
  - f. HR increase  $> 25\%$  to a HR  $> 100$  bpm

### Overall ECG interpretation

- Summary of ECG abnormalities will be produced on following variables: The number and percentage of subjects with newly occurring or persistent/recurrent on-treatment ECG abnormalities in overall ECG interpretation at any time point
    - The number and percentage of subjects with newly occurring or persistent/recurrent on-treatment ECG abnormalities by evaluation type and abnormality finding at any time point.
- If patients had at least once ECG abnormality at baseline, the baseline flag will be abnormal. Similarly, for post baseline visits, if patients had at least once ECG abnormality at a visit, then ECG is abnormal at that visit else normal.
- Patients with notable post-baseline ECG values will be listed. Box plots of ECG by scheduled visit and treatment for the parameters: QTcF and summary (mean) heart rate will be presented.

### 2.7.4.2 Vital signs

Vital signs measurements include systolic and diastolic blood pressure (SBP and DBP), pulse rate, height and body weight. Vital signs data taken on or after the time of the first intake of study drug and until 7 days after the last intake of study drug are regarded as on-treatment data. Vital signs data measured more than 7 days after last intake of study drug are regarded as post-treatment data and will not be summarized. All data will be included in the analyses regardless of rescue medication use.

The following analyses will be performed by treatment group:

- absolute on-treatment values and change from baseline summarized by parameter, and visit
- the number and percentage of patients with newly occurring or worsening notable vital signs on-treatment values (see [Table 6-5-1](#) for definition of notable values) summarized by parameter (except height), at any time on treatment considering all post-baseline data from scheduled, unscheduled and premature discontinuation visits
- Vital signs will also be summarized by clinically relevant categories:
  1. Pulse rate:  $< 40$  bpm,  $40 - 90$  bpm, and  $> 90$  bpm
  2. Systolic blood pressure:  $< 90$  mm Hg,  $90 - 140$  mm Hg, and  $> 140$  mm Hg

3. Diastolic blood pressure: < 50 mm Hg, 50 – 90 mm Hg, and > 90 mm Hg.

Number and percentage of patients with clinically relevant on-treatment vital signs values that occur at any time post-baseline will be summarized for minimum and maximum post-baseline values.

### **2.7.5 Renal events**

Summary of treatment emergent renal event overview data by treatment will be presented. All renal event overview data will be listed.

### **2.7.6 Liver events**

[figure not shown]
Summary of treatment emergent liver event overview data by treatment will be presented. All liver event overview data will be listed.

[figure not shown]
## **2.8 Pharmacokinetic endpoints**

[figure not shown]
Not Applicable

[figure not shown]
## **2.9 PD and PK/PD analyses**

[figure not shown]
Not Applicable

## **2.12 Interim analysis**

No interim analysis for efficacy is planned in this study. An independent, external DMC has been set up to review safety data (including specific safety summaries for adolescent participants) for this trial. No statistical adjustment will be made to the final analysis.

## **3 Sample size calculation**

The primary objective is to demonstrate that QAW039 150 mg is superior to placebo in pre-dose FEV1 following 12 weeks of post-baseline treatment. A difference of 112 mL in pre-dose FEV1 during treatment was assumed, which is similar to the model-averaged effect seen in

study QAW039A2206. The standard deviation (SD) of 380 mL and between-visit correlation for pre-dose FEV1 was based on study QAW039A2206 in a similar population. A treatment discontinuation rate of 15% was assumed based on QAW039A2206 and it was assumed that half of the patients discontinuing study treatment would have week 12 FEV1 values. Simulations were used to determine the sample size due to the complex J2R missing data imputation approach for the primary analysis.

Under the outlined assumptions, a sample size of 650 patients (325 per arm) would be needed to have 90% power to observe a statistically significant difference between QAW039 and placebo at the two-sided 5% significance level in the primary analysis as shown in [Table 3-1](#). The table also shows the sensitivity of the power to deviations from the assumptions.

